6.2.1 Efficacy Analysis

Endpoint	Statistical Analysis Methods
Primary	Two-sided two sample t-test, with analysis following the intention-to-treat principle and multiple imputation to deal with missing data.
Secondary (if applicable)	Linear mixed models for continuous and longitudinal data. Logistic regression for binary and longitudinal data. Log-rank test and Cox model for time-to-event data. Descriptive statistics for adherence and tolerability.

6.3 Other Analysis

Pharmacokinetic, pharmacodynamic, and biomarker exploratory analysis/analyses will be described in the statistical analysis plan and finalized before database lock. The population for pharmacokinetic analysis and pharmacodynamic analysis will be presented separately from the main clinical Trial report.

7 Data handling

[The investigator shall ensure that all procedures defined in this Protocol and in the Agreement are complied with, so that all data coming from the Participating site are reliable and have been processed correctly (especially the randomization lists) and shall ensure that the content of the case report form (CRF) shall accurately reflect source documents. Findings of the Study will be reported by the Participating Site through Investigator to Sponsor in the form of case reports. The collected data will be pseudonymized.]

7.1 Data Collection Tools and Source Document Identification

7.1.1 Operational aspects

Data collection, handling, processing and transfer for the purpose of this Trial will be performed in compliance with applicable regulations, guidelines for clinical trials and internal procedures.

7.1.1.2 *Data collection*

Source Data will be collected and recorded in the Trial participant's files/medical records.

Patient-related socio-demographic and health-related data will be gathered in the (e)CRF.

RedCAP will be used to capture study related data.

If applicable, worksheets may be used for capturing some specific data in order to facilitate completion of the (e)CRF. Any such worksheets will become part of the Trial participant's source documentation and will be filed together with or as part of the medical records (during but also following completion of the Trial).

It remains the responsibility of the Investigator to check that all data relating to the Trial, as specified in the Trial protocol, are entered into the (e)CRF in accordance with the instructions provided and that the forms are filled out accurately, completely and in a timely manner.

(e)CRFs are provided by the Sponsor for each participant. The Trial data will be transcribed from the source records (i.e. participant's medical file or Trial-specific source data worksheets) into an (e)CRF by Trial Staff. Transcription to the (e)CRF will be done as soon as possible after a participant visit and in a pseudonymized manner using a unique identifier assigned by the Sponsor.

The (e)CRFs will be available for review at the next scheduled monitoring visit (as applicable) and shall under no circumstances capture personal data such as but not limited to the participant or their relative(s) name, home address, contact details, full date of birth medical record number (e.g. UZ Leuven EAD number), social security number etc.

7.1.1.3 *Data Validation*

All data relating to the Trial must be prepared and validated by the Investigator. Any (e)CRF entries, corrections and alterations must be made by the Investigator or other authorized Trial staff.

Proper audit trails must be available to demonstrate the validity of the Trial data collected. This includes historical records of original data entries, by whom and when the data was entered, as well as detailed records of any corrections or additions made to the original data entry (i.e. who made the correction/addition, when and why), without obliterating the original data entry information.

7.1.1.4 *Data Management*

The Trial Data Manager will perform extensive consistency checks on the received data. Queries will be issued in case of inconsistencies in accordance with internal procedures.

7.1.1.5 *Data Transfer*

Any participant records or datasets that are transferred to the Sponsor or any partners of the Sponsor will contain the Trial-specific participant identifier only; participant names or any information which would make the participant identifiable will not be transferred. All pseudonymized data relating to the Trial must be transmitted in a secure manner to the Sponsor or any partners of the Sponsor (see 8.1.2. legal requirements).

7.1.2 *Legal requirements*

All source data will be kept at a secured location with restricted access at all times. These data must be collected and processed with adequate precautions to ensure confidentiality and compliance with applicable data protection laws and regulations and more in particular the EU General Data Protection Regulation 2016/679 (GDPR) and relevant national laws implementing the GDPR. Appropriate technical and organizational measures to protect the data against unauthorized disclosure or access, accidental or unlawful destruction, or accidental loss or alteration must be established. Trial staff whose responsibilities require access to personal data agree to keep the data confidential.

The Investigator and the Participating Site(s) (as applicable) shall treat all information and data relating to the Trial disclosed to them as confidential and shall not disclose such information to any third parties or use such information for any purpose other than the objectives of the Trial as described in this protocol. The collection, processing and disclosure of personal data, such as participant health and medical

information is subject to compliance with applicable laws and regulations regarding personal data protection and the processing of personal data.

The Investigator will maintain all source documents and completed (e)CRFs that support the data collected from each Trial participant, and will maintain a Trial Master File (TMF)/Investigator Site File (ISF) containing all Trial documents as specified in ICH-GCP E6(R2) Chapter 8 entitled “Essential Documents for the Conduct of a Clinical Trial”, and as specified by applicable regulatory requirement(s). The Investigator will take appropriate measures to prevent accidental or premature destruction of these documents.

Transfer of the pseudonymized data will be performed via a secured method of transfer taking into account all applicable security arrangements and regulations (such as the European General Data Protection Regulation). The receiving party will be bound by contractual agreement to keep the transferred data confidential at all times and to only process the data for the purpose of the Trial. To this end, appropriate Data Transfer Agreements (DTAs) will be established.

7.2 Audits and Inspections

The Investigator will permit direct access to Trial data and documents for the purpose of monitoring, audits and/or inspections by authorized entities such as but not limited to: the Sponsor or its designees and competent regulatory or health authorities. As such (e)CRFs, source records and other Trial related documentation (e.g. Investigator Site File, the Trial Master File, pharmacy records, etc.) must be kept current, complete and accurate at all times.

7.3 Monitoring

In accordance with GCP the Sponsor is responsible for monitoring the Trial to ensure compliance with GCP and current legislation, and to verify, among other requirements, that proper written informed consent has been obtained and documented, that the Trial procedures have been followed as shown in the approved protocol, and that relevant Trial data have been collected and reported in a manner that assures data integrity.

For those trials with UZ Leuven as Sponsor, UZ Leuven Clinical Trial Center (CTC) monitors only prospective interventional IMP/ IMD trials which are categorized as high risk trials, according to UZ/KU Leuven policy. Therefore, monitoring by CTC is not applicable for this study without IMP/IMD.

Hence, based on the above policy and as permitted by GCP, the Sponsor of the trial accepts the minimal risks associated with this trial and determines that monitoring activities (as defined by GCP) by a qualified individual, independent of the study team, is not necessary as it will provide little or no added value in protecting the safety of trial participants and assuring the integrity of collected trial data. Nonetheless, the UZ Leuven study team will take all possible measures to assure the quality and integrity of trial data and to safeguard the safety and wellbeing of trial participants, in accordance with the requirements set out in GCP.

7.4 Archiving

As specified in ICH-GCP E6(R2) section 8.1 Addendum, the Sponsor and Investigator/Participating Site will maintain a record of the location(s) of all respective Essential Trial Documents (including but not limited to Source Documents, completed and final (e)CRF and ISF/TMF). The Sponsor should ensure that the Investigator has control of and continuous access to the (e)CRF data reported to the Sponsor during the Trial.

The Investigator/Participating Site should have control of all Essential Documents and records generated by the Investigator/Participating Site before, during and following termination of the Trial.

The Sponsor is responsible for archiving Trial specific documentation (such as but not limited to the Trial protocol, any amendments thereto, the final Clinical Study Report (CSR) and the Trial database) according to ICH-GCP E6(R2). Source data and site-specific Trial documents (such as but not limited to the original signed ICFs) will be archived by the participating site(s) according to local practice, and for at least 25 years following termination of the Trial. Archived data may be held on electronic record, provided that media back-up exists, hard copies can be obtained, if required and measures are taken to prevent accidental or premature loss or destruction of data. Destruction of Essential Documents prior to, during or upon completion of the required archival period, will require written authorisation from the Sponsor.

8 Ethical and Regulatory Considerations

7.5 Ethics Committee (EC) review & reports

Before the start of the Study, this protocol and other related documents will be submitted for review to the EC for Study authorization. The Study shall not commence until such approvals have been obtained and until other relevant essential Study documents, such as duly signed contract agreements, evidence of adequate Study financing etc. are in place.

It is the responsibility of the CI to produce the Annual Progress Report (APR) and submit to the EC within 30 days of the anniversary date on which favourable opinion to start the Trial was given, and annually until the Trial is declared ended.

8.3 Regulatory Compliance

The Study will be conducted in compliance with ICH-GCP E6(R2) guidelines, other GxP guidelines, the most recent version of the Declaration of Helsinki, the Belgian law of May 7th 2004 regarding experiments on the human person (as amended) and with the EU General Data Protection Regulation 2016/679 (GDPR), the relevant Belgian laws implementing the GDPR, the Belgian Law of August 22nd 2002 on patient rights and all other applicable legal and regulatory requirements.

8.4 Protocol / GCP compliance

The Study must be performed in accordance with the protocol, current ICH and ICH-GCP guidelines, and applicable regulatory and country-specific requirements. ICH guidelines are an international ethical and scientific quality standard for designing, conducting, recording, and reporting studies that involve the participation of human participants. Compliance with this standard provides public assurance that the rights, safety, and well-being of Study participants are protected, consistent with the principles that originated in the most recent version of the Declaration of Helsinki, and that the Study data are credible, reliable and reproducible.

The Investigator and Trial team acknowledge and agree that prospective, planned deviations or waivers to the protocol are not permitted under applicable regulations on clinical studies. However, should there be an accidental protocol deviation, such deviation shall be adequately documented in the source documents and on the relevant forms and reported to the CI and Sponsor. Deviations should also be reported to the EC as part of the EC's continued review of the Trial (e.g. through the ASR, APR, etc.). Protocol deviations which are found to frequently recur, will require (immediate) action. The Investigator acknowledges that such recurring protocol deviations could potentially be classified as a serious violation of ICH and/or the protocol.

It is understood that "a serious violation" is likely to affect to a significant degree:

- the safety or physical or mental integrity of the Trial participants; or
- the scientific validity of the Trial

The Investigator is expected to take any immediate action required to protect the safety of any participant included in the Trial, even if this action represents a deviation from the protocol. In such cases, the Sponsor should be notified of this action and the EC at the Trial site should be informed according to local procedures and regulations.

8.5 Data protection and participant confidentiality

The Study will be conducted in compliance with the requirements of the EU General Data Protection Regulation 2016/679 (GDPR), and the relevant Belgian laws implementing the GDPR including the Belgian Privacy Act of 30 July 2018 on the protection of privacy in relation to the processing of personal data. Any collection, processing and disclosure of personal data, such as participant health and medical information is subject to compliance with the aforementioned personal data protection laws (cfr. Data Processing Annex (DPA) in Appendix 1). In case personal data is transferred outside the European Economic Area, safeguards will be taken by the Sponsor to ensure that appropriate protection travels with the data in accordance with the GDPR. (https://ec.europa.eu/info/law/law-topic/data-protection/international-dimension-data-protection/rules-international-data-transfers_en#documents)

Any personal data shall be treated as confidential at all times including during collection, handling and use or processing, and the personal data (including in any electronic format) shall be stored securely at all times and with all technical and organizational security measures that would be necessary for compliance with EU and national data protection legislation (whichever is more stringent). The Sponsor shall take appropriate measures to ensure the security of all personal data and guard against unauthorized access thereto or disclosure thereof or loss or destruction while in its custody.

8.6 Insurance

The Participating Site, the Investigator and Sponsor shall have and maintain in full force and effect during the term of this Trial, and for a reasonable period following termination of the Trial, adequate insurance coverage for: (i) medical professional and/or medical malpractice liability, and (ii) general liability.

For Belgian Participating Sites

Art 29 of the Belgian Law relating to experiments on human persons dated May 7th, 2004 applies. Prior to the start of the Trial, the Sponsor shall enter into an insurance contract in order to adequately cover Trial participants from Belgian sites in accordance with art. 29 of the said law.

8.7 Amendments

Unless for urgent reasons as specified in ICH-GCP E6(R2) section 4.5.4, amendments must not be implemented prior to EC review and/or approval.

In accordance with the Belgian law of May 7th 2004 regarding experiments on humans, the Sponsor may develop a non-substantial amendment at any time during the Trial. If a substantial amendment to the clinical Study agreement or the documents that supported the original application for the clinical Trial authorisation is needed, the Sponsor must submit a valid substantial amendment to the EC for review and approval. The EC will provide a response in accordance with timelines defined by applicable regulations. It is the Sponsor's responsibility to assess whether an amendment is substantial or non-substantial for the purpose of submission to the EC.

Amendments to the Study are regarded as 'substantial' when they are likely to have a significant impact on the safety or physical or mental integrity of the clinical Study participants, or the scientific value of the Study.

https://ec.europa.eu/health/sites/health/files/files/eudralex/vol-10/2010_c82_01/2010_c82_01_en.pdf

8.8 Post-Trial activities

After completing the clinical trial, participants will not be provided with study medication nor VLCKD. The study drug and VLCKD programs are approved and available to patients on the Belgian market, at own expense, and after medical advice and prescription as needed.

9 Human Body Material

The investigator and study team will comply with all applicable laws and patient and privacy rights and all applicable laws regarding the use of human body material (HBM) when collecting, processing, storing and/or using samples of HBM for scientific research..

Particularly, the investigator shall act in accordance with the Law of 19 December 2008 regarding the procurement and use of human biological material intended for human medical applications or for scientific research purposes and its royal decree. To this end, the investigator will obtain approval from the notified UZ/KU Leuven Biobank prior to the start of the research. The investigator and his team shall ensure the traceability of the HBM during the complete lifecycle of the HBM.

The investigator will use the HBM for the purposes as described in the Protocol. If the HBM is to be used for any other purposes than those stated in the Protocol, the investigator shall first obtain approval from the UZ/KU Leuven Biobank and the appropriate Ethics Committee (EC).

The Participating Site warrants that these Samples have been collected in accordance with the legislation in force in the country of origin and in accordance with the (inter)national standards on ethics and protection of privacy and personal data, and can be legitimately used for the Study. The providers of the Samples in particular warrant that the donor has consented to the use of his/her Samples for the Study and/or has not objected to it to the extent required under the legislation in force in the country of origin. Since UZ Leuven will receive coded/pseudonymized Samples from the Participating Site/Collaborating Hospital, UZ Leuven is subject to the rights and obligations as 'data controller' set forth under GDPR in relation to the processing of Personal Data. The providers of the Samples are subject to the rights and obligations as 'data processor' set forth under the GDPR in relation to the processing of Personal Data. UZ Leuven and the providers of the Samples' rights and obligations with respect to Personal Data are further detailed in the data processing agreement attached in Addendum I.

10 Research Registration, Dissemination of Results and Publication Policy

The Declaration of Helsinki (latest version) and European and Belgian regulations require that every research Study involving human participants be registered in a publicly accessible database before recruitment of the first participant. The CI is responsible for registering the Study.

In addition, the CI will fulfil their ethical obligation to disseminate and make the research results publicly available. As such the CI is accountable for the timeliness, completeness and accuracy of the reports. Researchers, authors, Sponsors, editors and publishers must adhere to accepted guidelines for ethical reporting. Negative and inconclusive, as well as positive results must be published or otherwise made publicly available. Sources of funding, institutional affiliations and conflicts of interest must be declared in publication.

[Publications will be coordinated by the CI. Authorship to publications will be determined in accordance with the requirements published by the International Committee of Medical Journal Editors and in accordance with the requirements of the respective medical journal.

For multicentre Trials, it is anticipated that the primary results of the overall Trial shall be published in a multicentre publication.

Participating Sites are not allowed to publish any subset data or results from the Trial prior to such multicentre publication.

Any publication by a Participating Site must be submitted to the Sponsor for review at least thirty (30) calendar days prior to submission or disclosure. Sponsor shall have the right to delay the projected publication for a period of up to three (3) months from the date of first submission to the Sponsor in order to enable the Sponsor to take steps to protect its intellectual property rights and know-how.]

11 Intellectual Property

Any know how, inventions, methods, developments, innovations, discoveries and therapies, whether patentable or not, arising from the Trial or made in the performance of the Trial protocol ("Inventions") shall vest in the Sponsor. The Participating Site, its employees and Investigator(s) shall promptly disclose to the Sponsor any such Inventions. Parties have expressly agreed that any and all Trial data as collected and prepared in the performance of the Trial protocol shall be the sole property of Sponsor unless otherwise agreed in the clinical trial agreement.

12 References

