Procedures/assessments	Phase 0: Screening and randomization		Phase 1: Lifestyle + NB with vs without VLCKD							Phase 2: Lifestyle + NB (all participants)				Follow-up (all participants)		
	Screening (In-clinic)	Randomization (in-clinic)	Remote	Remote	Remote	Remote	Remote	Remote	In-clinic (study specific)	Remote	Remote	In-clinic (Routine)	Remote	Remote	In-clinic (study specific)	In-clinic (routine)
Visit	V1	V2	V3	V4	V5	V6	V7	V8	V9	V10	V11	V12	V13	V14	V15	V16
Timing of visits (weeks)		Start	Start	W3	W4	W6	W8	W10	W10	W12	W16	W16	W20	W26	W26	W52
Visit window (days)									±30			±30			±30	±30
Lifestyle program			X		X		X			X	X		X	X		
Naltrexone/bupropion (NB)		X							X			X			X	X
VLCKD			(X) ¹	(X) ¹	(X) ¹	(X) ¹	(X) ¹	(X) ¹								
Screening assessments and randomization																
Informed consent	X ²															
Inclusion/exclusion criteria	X	X														
Randomization		X														
Anthropometric data (height, weight, waist circumference)		X							X			X			X	X

Clinical examination (Blood pressure, heart and lung auscultation, abdominal palpitation and percussion)		X							X			X				X	X
Laboratory tests																	
Fasting glucose		X							X			X				X	X
Hemoglobin A1c		X										X					X
Lipids: LDL-cholesterol, HDL-cholesterol, triglycerides		X							X			X				X	X
Liver test: AST, ALT, gamma-GT, alkaline phosphatase, total bilirubin, albumin		X										X					X
Kidney function: creatinine, eGFR		X										X					X
Thyroid function: TSH, free T4		X										X					X
Uric acid		X										X					X
Questionnaires																	
The PsyEndoAUDIT questionnaire ³		X							X			X				X	X
The PsyEndoCIDI questionnaire ³		X							X			X				X	X
The PsyEndoEDE questionnaire ³		X							X			X				X	X
The PsyEndoHADS questionnaire ³		X							X			X				X	X
Nederlandse vragenlijst voor eetgedrag ³		X							X			X				X	X
The ObesitasIPAQ questionnaire ³		X							X			X				X	X

The quality of life (SF-36) questionnaire ³		X							X				X			X	X
The outtake questionnaire															X		
Reason for discontinuation		X							X			X			X	X	
(Serious) Adverse event (S)(AE) assessment		X							X			X			X	X	

- Depending on randomization in either intervention (with VLCKD) or comparator group (without VLCKD).
- Informed Consent must be obtained prior to performing any other Trial-related procedures as part of the standard of care.
- See appendix 4 for the respective questionnaires.

I Background and Rationale

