2.3 Secondary Endpoints

- A weight loss percentage at 10 weeks, 16 weeks and at end of trial (= 52 weeks from start)
- A proportion of patients with a weight loss percentage of 5% or more at 10, 16, 26 and 52 weeks
- A proportion of patients with a weight loss percentage of 10% or more at 10, 16, 26 and 52 weeks
- The time to reach a weight loss percentage of 5% and 10%
- The dose of naltrexone/bupropion used at 10, 16, 26 and 52 weeks and at the end of the trial
- The tolerability of VLCKD and NB
- Adherence to VLCKD and NB
- The Patient-Reported Outcome Measures (PROMs) of hunger and cravings at 0, 4, 10, 16, 26 and 52 weeks
- The change in fasting glucose, lipids and blood pressure at 10, 16, 26 and 52 weeks]

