2.4 Study design

This is a parallel multicentric longitudinal randomized controlled trial in which prospective data will be collected from the electronic health record. The inclusion and exclusion criteria will be checked and afterwards patients will be randomized to (unblinded) medication only or combination with VLCKD. Both groups include NB and lifestyle changes for 26 weeks but the patients belonging to the experimental group must follow a VLCKD in the first 10 weeks on top of it. Like the other group, the remaining 16 weeks will consist of NB combined with lifestyle interventions. Afterwards there is a follow-up extension of 26 weeks. See appendix 4 for detailed overview of clinical and biochemical parameters to be collected during the trial.

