2.5 Expected duration of the Study

[This trial will have a duration of 2 years in total. 1 year is taken into account to include the patients into the study according to the inclusion and exclusion criteria. Afterwards patients will be randomly inserted into the comparator arm (NB + lifestyle interventions) or experimental arm (NB + Lifestyle interventions + VLCKD). Both arms of the study design will be evaluated for 52 weeks. 26 weeks will consist of the treatment after which another 26 weeks will be used as a follow-up extension.]

The End of Study is defined as Last Patient Last Visit (LPLV). The CI shall notify the EC of the end of the Study. The CI will submit a final report with the results of the study, including any publications/abstracts, to the EC within 1 year of study termination.

The Sponsor or EC can decide to halt or prematurely terminate the Study when new information becomes available whereby the rights, safety and well-being of Study participants can no longer be assured, when the integrity of the Study has been compromised, or when the scientific value of the Study becomes obsolete and/or unjustifiable]

3 Study Population / Eligibility Criteria

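### The protocol is inconsistent on naltrexone/bupropion between weeks 26 and 52, so the background treatment behind the week-52 secondary endpoints is not fixed

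*Protocol*

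**What the plan says.** Two groups of statements in the protocol bear on NB after week 26.

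**Pointing to a 26-week treatment period**
- Section 2.4: "Both groups include NB and lifestyle changes for 26 weeks", and then "Afterwards there is a follow-up extension of 26 weeks".
- Section 2.5: "26 weeks will consist of the treatment after which another 26 weeks will be used as a follow-up extension".
- Study flowchart, phase labels: NB is named in the labels of phases 1 and 2. The last block is labelled as follow-up only.

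**Pointing to NB up to week 52**
- Study flowchart, NB row: marked at the start and at the in-clinic visits of weeks 10, 16, 26 and 52.
- Section 2.3, as an endpoint: "The dose of naltrexone/bupropion used at 10, 16, 26 and 52 weeks and at the end of the trial". The same list equates the end of the trial with week 52.
- Section 4.5: the week-52 visit is one of three visits called routine for NB.
- Section 4.7: the full dose applies from week 4 onward, with no stop week.
- Section 8.8: "After completing the clinical trial, participants will not be provided with study medication nor VLCKD". It adds that the drug is then available at the patient's own expense.

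On timing, the flowchart gives ±30 days for the in-clinic visits at weeks 10, 16, 26 and 52. The primary weight is measured at the week-26 visit (section 2.2).

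**The concern.** The treatment schedule is something a protocol has to settle itself. It cannot be left to an analysis plan. Here a site cannot tell from the text whether NB after week 26 is stopped, supplied or left to the patient to buy.

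Three kinds of week-52 endpoint depend on the answer: percentage weight loss, the 5% and 10% responder proportions, and the NB dose. If NB has stopped, the week-52 weight describes durability off drug. If it continues, the weight describes a year on drug. The dose endpoint is either a tolerated dose, zero by design, or a record of who chose to buy. NB adherence after week 26 likewise has no standard to be judged against.

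The wide visit windows raise a smaller question: whether the week-10 and week-16 measurements are distinct time points, and whether the week-26 weight is always taken within the treatment period.

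**Working it through.** **1. Length of the unsettled period.** Sections 2.4 and 2.5: 26 weeks treatment + 26 weeks extension = 52 weeks. The unsettled part is 26/52 = 50% of each patient's time on study.

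**2. Does one reading satisfy every section?**

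| Provision | A: NB stops at week 26 | B: NB supplied to week 52 | C: supply ends at week 26, self-paid use possible |
|---|---|---|---|
| 2.4 and 2.5, 26 weeks of treatment | fits | conflicts | fits |
| Flowchart, last block is follow-up only | fits | conflicts | fits |
| Flowchart, NB marked at week 52 | no evident purpose | fits | fits if the mark means review of use |
| 2.3, NB dose at week 52 | zero by design | fits | fits, but measures purchase |
| 4.5, week 52 routine for NB | no evident purpose | fits | fits |
| 4.7, no stop week | stop not stated | fits | end of supply not stated |
| 8.8, no supply after the trial | silent on week 26 | fits | own-expense use mentioned only for after the trial |

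Readings A and B each clash with some of the text. Reading C clashes least, but no section states it.

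**3. Visit windows.** Nominal day = week × 7; window = nominal day ± 30.
- Week 10: 70 ± 30 = days 40 to 100.
- Week 16: 112 ± 30 = days 82 to 142.
- Week 26: 182 ± 30 = days 152 to 212.
- Week 52: 364 ± 30 = days 334 to 394.

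Weeks 10 and 16 are 112 − 70 = 42 days apart, and their windows share days 82 to 100, which is 100 − 82 + 1 = 19 calendar days. Windows of ±w are disjoint only if 70 + w < 112 − w, so w < 21. At ±21 both include day 91 (70 + 21 = 112 − 21). At ±20 they end at day 90 and begin at day 92.

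The week-26 window runs to day 212, which is 30 days (30/7 = 4.3 weeks) past day 182.

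**4. What late week-26 visits could do to the primary test.** Section 6.1 assumes means of 6.75% (SD 7.12) and 12% (SD 5.3), so the difference is 5.25 points. A two-sided 5% t-test with 80% power needs 24 per arm. With 20% drop-out, 24/0.8 = 30 per arm, or 60 in total, within two patients of the stated 62.

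Evaluable patients: 31 × 0.8 = 24.8, taken as 25 per arm. The standard error is √((7.12² + 5.3²)/25) = 1.775, and Welch power is 0.825.

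The documents give no regain rate, so what follows is assumption:
- Half the visits late by 0 to 30 days (uniform), with regain of r points per 30 days, equal in both arms. Each arm mean moves by 0.25r and each variance grows by r²/6 − (0.25r)². For r = 0.5, 1 and 2, power is 0.824, 0.824 and 0.821.
- If instead the difference between arms itself shrank by 0.5, 1 or 2 points, power would be 0.74, 0.65 or 0.43. Nothing in the documents indicates such a loss.

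**The case against.** The best defence is that sections 2.4, 2.5 and the flowchart's phase labels agree on 26 weeks, and that the opposing evidence is indirect. Section 8.8 says what is not provided after the trial; it does not promise supply until then. Section 2.3 concerns the dose used, not the dose supplied. The flowchart marks NB at the same in-clinic visits as body measurements, although the drug is taken between visits, so the mark may mean a review of use. At week 52 it can hardly mean supply, since section 8.8 ends supply there. This makes reading C plausible, but it has to be inferred. Section 4.5 and the missing stop week still pull the other way.

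A reader might infer three stronger things that the documents do not support.

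- **That the primary weight is taken after treatment has ended.** For NB this requires both the 26-week reading and a stop at day 182 rather than at the week-26 visit. NB is marked at that visit and its dose there is an endpoint, which fits use up to the visit. Under either reading only the lifestyle programme is scheduled to end at about month 6 (Appendix 3), and it does so in both arms.
- **That the two sites will diverge.** Nothing says so, and the funding section has the same company supplying both.
- **That the week-52 comparison is invalid.** NB is common to both arms and section 6.2 applies intention to treat regardless of adherence, so the randomised contrast can still be estimated.

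On the windows, no text assigns weights to time points by calendar date, and handling of out-of-window visits may be in the analysis plan. That limits the point to good practice, but the overlap is fixed in the protocol itself.

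**Conclusion.** The point holds as an inconsistency about NB in weeks 26 to 52, half of each patient's time on study. It leaves the background treatment behind the week-52 secondary endpoints unfixed and the week-52 dose endpoint without a clear meaning. It does not invalidate the randomised comparison, and it leaves the week-26 primary endpoint largely unaffected. That last statement assumes any drift after day 182 is similar in the two arms; the documents give no figure from which a bias could be derived.

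The window matter is secondary: an overlap of 19 calendar days between weeks 10 and 16, and a week-26 window reaching 30 days beyond the nominal end of the programme. The protocol should be amended on NB, because NB status that is not recorded as it happens may be hard to recover later.

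**What to change.** 1. Reconcile the flowchart and sections 2.3, 2.4, 2.5, 4.5, 4.7 and 8.8 into one statement on NB status and supply from week 26 to week 52. Which arrangement applies is for the sponsor to decide.
2. At weeks 26 and 52, record the NB source (supplied, self-paid, none) and the last-dose date. Dose and adherence are already planned endpoints, so these are the only additions.
3. Report NB use at week 52 by arm, descriptively. Do not compare treatments within groups defined by NB use: it arises after randomisation and the diet may influence it.
4. Narrow the week-10 and week-16 windows to at most ±20 days so that they do not overlap.
5. Once item 1 is settled, state the timing of the week-26 weight relative to the end of treatment.

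The cost is protocol wording, two eCRF fields and slightly tighter scheduling at weeks 10 and 16. The sample size does not change.
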